The study included a total of 32 volunteers between the ages of 65-80, who stayed in Karaman Ahmet Mete Nursing Home, Elderly Care and Rehabilitation Center, with mild or moderate Alzheimer's dementia diagnosed by a neurologist. There were 90 older people in Karaman Ahmet Mete Nursing Home, Elderly Care and Rehabilitation Center. Power analysis was performed to determine the size of the sample to be included in the study. As a result of the power analysis, assuming that the effect size to be obtained between the two groups will be large ($d = 0.9$), when at least 32 individuals (at least 16 individuals per group) were included in the study, it was calculated that 80% power could be obtained at 95% confidence level (with 0.05 error margin). As a result of the power analysis, it was calculated that at least 16 individuals could be included in each group (at least 32 individuals in total). 20% risk rate was determined for the individuals who could leave the study, 3 individuals were added to each group, and the study was organized with 19 individuals in each group. However, these people were excluded from the study as 4 people were not meeting inclusion criteria, 2 people were declined to participate, and therefore the study was completed with 32 individuals (Figure 1). The study included volunteers between the ages of 65-80 with mild or moderate AD diagnosis, who did not have any difficulty or problems in communicating, who did not have any neurological diseases that disrupt balance and coordination such as a cerebrovascular event, Parkinson's disease, Multiple Sclerosis, and neurological disorder, who obtained a score of 18 - 24 points in the Mini-Mental State Test (MMST) were included in the study. Patients diagnosed with rapidly progressing dementia (infection, vascular, hematologic diseases), those who could not be contacted during the follow-up period or who did not participate in the training session, those who experienced cardiac and cerebrovascular events, endocrine disorders, fluid-electrolyte imbalance and infection, those with malignancy and those who received chemotherapy and radiotherapy that causes malignancy, delirium or depression and malignant sensory loss (those with the Semmes-Weinstein monofilament thickness of 4.56 and above), and those with a lower or upper extremity amputation at any level were excluded from the study.

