The data were analyzed using the SPSS 24.0 packaged software. Continuous variables were presented as mean \pm standard deviation, median (minimum and maximum values), while categorical variables as number and percentage. The suitability of the data for normal distribution was examined by the Shapiro-Wilk test. The significance test of the difference between the two means was used in comparing the independent group differences when the parametric test assumptions were provided, and the Mann-Whitney U test was used in comparing the independent group differences when the parametric test assumptions were not provided. The significance test of the difference between the two pairs was used in comparing the dependent group differences when the parametric test assumptions were provided, and the Wilcoxon two-pPaired sample test was used when the parametric test assumptions were not provided. Differences between categorical variables were analyzed by chi-square analysis. In all analyses, $p<0.05$ was accepted as statistically significant.

Results

The mean age of the individuals was 73.13 ± 3.54 years, and the mean age of the training group was 73.75 ± 5.16 years. No statistically significant difference was found between the groups in terms of age, gender, height, weight, body mass index, occupation, marital status, education level, income level, number of children, and social security ($p>0.05$).

Upon examining the MMST values, the difference between the 2 groups was not statistically significant ($p>0.05$). In the post-training measurements, the values of the training group were significantly higher compared to the control group ($p<0.05$). When the changes in the groups before and after the training were examined, no statistically significant change was observed in the control group, whereas the values of the training group were significantly higher after the treatment ($p<0.05$).

When the right and left knee extension muscle strength values of individuals with AD were examined, the difference between the 2 groups was not statistically significant before and after the training ($p>0.05$). When the changes of the groups before and after the training were examined, there was no significant change in the control group, whereas the values of the training group were significantly higher after the training ($p<0.05$).

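### The stated 80% power at 16 per group matches a one-sided 0.05 t-test, which the plan never declares; a two-sided test gives about 69%

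*Combined protocol and SAP*

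**What the plan says.** The sample-size paragraph in Study Procedure and Protocol powers a comparison between the two arms, "assuming that the effect size to be obtained between the two groups will be large", and sets d = 0.9. It then says that when "at least 32 individuals (at least 16 individuals per group) were included in the study, it was calculated that 80% power could be obtained". The error level comes in the same sentence: "80% power could be obtained at 95% confidence level (with 0.05 error margin". The paragraph names no test and does not say whether 0.05 is one-sided or two-sided.

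Three people per arm were added for possible losses, so that "the study was organized with 19 individuals in each group". After exclusions and refusals "the study was completed with 32 individuals", which is exactly the calculated minimum.

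The Statistical Analysis Plan gives the parametric between-group test: "The significance test of the difference between the two means was used in comparing the independent group differences". Mann-Whitney U is the fallback. It adds that "Differences between categorical variables were analyzed by chi-square analysis" and closes with one rule: "In all analyses, $p<0.05$ was accepted as statistically significant". Sidedness is not stated there either.

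**The concern.** An effect of d = 0.9 with 16 per group looks too small a design for 80% power under an ordinary two-sided 5% test. The question is which test produces the stated figure, and whether the document declares that test.

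The power statement is the only reason given for the sample size. After training, the Results report no significant between-group difference in knee extension strength, TFES or TUG. Strength and fall risk are the outcomes named in the study's purpose. A reader who takes 80% power at face value would put the chance of missing an effect of the planned size at 20%. If the tests were two-sided, it is about 31%.

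**Working it through.** **Inputs.** From the power paragraph: d = 0.9, 16 per group, 1:1 allocation, level 0.05. From the Statistical Analysis Plan: an unpaired comparison of two means. Sidedness is given in neither place.

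**Method.** Two-sample t-test, noncentral t distribution, with df = 2 × 16 − 2 = 30 and noncentrality d × √(n/2) = 0.9 × √8 = 2.546.

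**Reproducing the plan's figure.** With one-sided alpha 0.05, power at 16 per group is 0.8003. At 15 per group it is 0.776. So 16 is the smallest group size that reaches 80% (required n = 15.99), and the stated figure is recovered exactly.

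**Two-sided at 0.05.**

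| n per group | One-sided power | Two-sided power |
|---|---|---|
| 15 | 77.6% | 66.3% |
| 16 | 80.0% | 69.3% |
| 19 | 85.9% | 77.0% |
| 20 | 87.5% | 79.2% |
| 21 | 88.9% | 81.2% |

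- Type II error at 16 per group: 1 − 0.693 = 0.307.
- Two-sided 80% power: required n = 20.39, so 21 per group and 42 in total.
- Effect detectable with 80% two-sided power at 16 per group: d = 1.02.
- Two-sided alpha at which 16 per group gives 80% power: 0.0998, which corresponds to 90% confidence.

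**Could another two-sided method have given 16 per group?**

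- Normal approximation: 2 × (1.960 + 0.842)² / 0.9² = 19.4, so 20 per group. Power at 16 is 72.1%.
- Mann-Whitney U with normal data (relative efficiency 3/π): 22 per group. Power at 16 is 67.1%. Other distributional assumptions give 24 (minimum efficiency), 19 (logistic) or 14 (Laplace). None gives 16.
- Paired t-test with 16 people: power 92%. It is also not the comparison that was powered.
- Baseline-adjusted comparison: this reaches 80% only if the baseline-outcome correlation is about 0.48. The document states no correlation and describes no adjustment. As an assumed range, correlations of 0.3 to 0.6 give 73% to 87%.

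On the one-sided side, the normal approximation gives 81.6% and Mann-Whitney with normal data gives 78.3%, both close to 80%. The one-sided t-test is the exact match.

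**Precision at 16 per group.** The 95% confidence interval for a between-group mean difference has half-width t(30) × √(2/16) = 2.042 × 0.354 = 0.72 SD.

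**The case against.** The strongest reply is that the arithmetic is right. With the plan's inputs and a one-sided 0.05 test, 80% at 16 per group is correct, so the fault is an omitted word and not a wrong number. The two-sided reading is also inferred. A 95% confidence level fixes alpha but not the number of tails, the name of the t-test fits either, and the chi-square sentence says nothing about how a mean difference was powered. The authors never use the 80% figure to interpret a result, and d = 0.9 is tied to no particular endpoint. Data collection is over, so no design decision can change.

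Much of this stands. Sidedness is not stated, so the 69% is conditional on the two-sided reading, and a 31% type II error cannot be assigned to any one outcome. The 77.0% at 19 per group is a side point, because the plan claims 80% at 16. The TFES and TUG sentences report p>0.05 beside the statement of no difference, so changing them is a small matter of wording.

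It does not remove the problem. A single p<0.05 rule for every analysis, including baseline comparisons with no hypothesised direction, is most naturally two-sided. A one-sided answer would need a correction too. The Abstract reports p = 0.049 for the between-group MMST comparison in favour of training. If that were a one-sided t-test value, the two-sided value would be about 2 × 0.049 = 0.098.

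**Conclusion.** The concern holds. The stated power depends on a one-sided 0.05 test that the document does not declare. On the ordinary two-sided reading, the design has 69.3% power for d = 0.9, about 11 points below the claim. The completed sample is 10 people short of the 42 needed for two-sided 80% power.

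This rests on a two-sample t-test, equal groups, no baseline adjustment and two-sided testing at 0.05. The first three follow the plan's description; the last is inferred from its wording. The computation is certain, but which test the authors had in mind is not. The practical effect is limited to how much weight the non-significant between-group results for strength, TFES and TUG can bear. No reported estimate changes.

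**What to change.** 1. State whether the power calculation and the tests were one-sided or two-sided.
2. Unless the tests were in fact one-sided, replace the power sentence with: 16 per group gives about 69% power for d = 0.9 at two-sided alpha 0.05; 80% power requires d of about 1.02. If they were one-sided, say so, give the direction and label the reported p-values accordingly.
3. Report the between-group differences in knee extension strength, TFES and TUG with 95% confidence intervals from the existing data.
4. As a minor edit, describe TFES and TUG as not significantly different between groups. The strength sentence already does this and needs no change.

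The cost is a text correction and a short reanalysis of data in hand, with no further patients. The drawback is that the stated power becomes less favourable and the intervals will be wide, about ±0.72 SD.

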Among the 38 individuals with AD diagnosis, 1 individual was not included in the study after the first evaluation due to the MMST score lower than 18, 3 individuals were not included in the study due to the hearing and communication problems, and 2 individuals were not included because they did not want to start the study. The first evaluation of the patients was

performed before randomization. 32 individuals suitable for the criteria were included in the study (Figure 1). Randomization was performed by the sealed-envelope method. According to this method, 4 females and 12 males were determined to be in the control group, while 5 females and 11 males were determined to be in the training group.

The evaluation was completed before the intervention. The same evaluation was conducted after 6 weeks. The physiotherapist with more than 5 years of experience conducted all the evaluations. Exercise training was given by another 2-year experienced physiotherapist. The training group was trained with games from different categories such as balance and aerobic exercises with a Nintendo Wii virtual reality device 2 times a week for a period of 6 weeks, with 1 session lasting for 30 minutes, and each patient was trained with the same games. In the control group, no application was performed during this period, and routine medical treatments were continued. The training group was evaluated before and after the training, while the control group was re-evaluated at the end of the 6th week after the first evaluation. After the study was completed, the volunteers from the control group were also given training.

In order to determine the sociodemographic characteristics of individuals, the case report form included questions about name and surname, age, height, weight, body mass index, dominant side, smoking, alcohol use, previous occupation, marital status, educational status, income level, number of children, social security, special healthcare needs, number of falls in the last year, vision problems, personal history, family history, medicines used, surgeries undergone, and use of a walking stick.

Their cognitive status was evaluated by the MMST. According to the MMST, 24-30 points were considered as normal cognitive levels, 18-23 points were considered as mild cognitive disorders, and 0-17 points were considered as severe cognitive disorders.

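### The 20% drop-out allowance (19 per group) was used up by exclusions before randomisation; exactly the minimum of 16 per group was randomised, with no reserve left

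*Combined protocol and SAP*

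**What the plan says.** All the relevant text on numbers is in the section Study Procedure and Protocol of the combined protocol and SAP.

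The sample size paragraph gives the power analysis: "assuming that the effect size to be obtained between the two groups will be large ($d = 0.9" and "80% power could be obtained at 95% confidence level (with 0.05 error margin". The result is that "at least 16 individuals could be included in each group (at least 32 individuals in total". A 20% risk is then set for people who might leave, and the paragraph continues: "3 individuals were added to each group, and the study was organized with 19 individuals in each group". The next sentence explains the fall from 38 to 32: "4 people were not meeting inclusion criteria, 2 people were declined to participate".

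The participant flow paragraph describes the same six people in more detail. It begins "Among the 38 individuals with AD diagnosis" and lists 1 person with a Mini-Mental score below 18, 3 with hearing or communication problems and 2 who did not wish to start. It says that the first evaluation came before randomisation and that "32 individuals suitable for the criteria were included in the study". Allocation is reported as 4 women and 12 men to control, and 5 women and 11 men to training.

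The Statistical Analysis Plan says "In all analyses, $p<0.05$ was accepted as statistically significant". Neither section says whether the tests, or the power calculation, are one-sided or two-sided.

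**The concern.** A drop-out allowance protects the power calculation against people lost after they have been allocated. People found ineligible or unwilling before allocation are a recruitment matter and need a separate allowance. Here one set of six places serves both purposes. The sample size paragraph introduces them as cover for people leaving the study, then spends them on people who never entered a group.

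Two stated design properties are at stake: the size of each group (19) and the protection against 20% loss. If neither was delivered, the trial started at its own minimum, and one loss from either group would have taken it below that. The plan did foresee such losses. Its exclusion list includes people who could not be reached during follow-up or who did not attend training, which can only happen after enrolment.

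**Working it through.** **Inputs.** From the sample size paragraph: d = 0.9, 80% power, alpha 0.05, minimum 16 per group, 20% loss, 3 added per group, 19 per group. From the participant flow paragraph: 38 people with the diagnosis; 1 + 3 + 2 not included; 4 + 12 and 5 + 11 allocated. Sidedness is not stated, so both cases are shown.

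**1. Reproducing the minimum of 16.** For two equal groups of n, the t statistic is noncentral t with 2n − 2 degrees of freedom and noncentrality d × √(n/2). At n = 16 the noncentrality is 0.9 × √8 = 2.546 on 30 degrees of freedom.
- One-sided 0.05: critical value 1.697, power 80.0%. This reproduces the stated 16.
- Two-sided 0.05: critical value 2.042, power 69.3%. Two-sided 80% needs 20 per group by the normal approximation, or 21 by the t calculation (79.2% at 20, 81.2% at 21).

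**2. Reproducing the 19.** A simple uplift gives 16 × 1.20 = 19.2, which is 19 if rounded down. So 19 can be traced, but this uplift does not preserve 16 after the loss:
- Needed: 16 / (1 − 0.20) = 20 per group, 40 in total.
- From 19: 19 × 0.80 = 15.2, below 16.
- Loss that 19 can absorb: 3/19 = 15.8%.

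The shortfall is one person per group.

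**3. Following the 38.**
- Sample size paragraph: 19 + 19 = 38, and 38 − 4 − 2 = 32.
- Participant flow paragraph: 38 − (1 + 3 + 2) = 32.
- Allocation: 4 + 12 = 16 control and 5 + 11 = 16 training, total 32.

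The two accounts agree on the counts and on the people: 1 + 3 = 4 ineligible, and 2 declined. The first evaluation preceded randomisation, and the allocated numbers sum to 32, not 38. All six were therefore outside the randomised set. The reserve after randomisation was 16 − 16 = 0 per group.

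**4. What a 20% loss would have meant.** 16 × 0.80 = 12.8, so 12 to 13 per group. Power at d = 0.9, alpha 0.05, noncentral t:

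| Per group | One-sided | Two-sided |
|---|---|---|
| 16 | 80.0% | 69.3% |
| 15 | 77.6% | 66.3% |
| 13 | 72.1% | 59.6% |
| 12 | 68.8% | 55.9% |

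The cost of the loss is about 8 to 11 percentage points one-sided (80.0 − 72.1 = 7.9; 80.0 − 68.8 = 11.2) and about 10 to 13 two-sided (69.3 − 59.6 = 9.7; 69.3 − 55.9 = 13.4).

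**5. Detectable effect with 16 per group.** Solving the two-sided 0.05 calculation for 80% power gives d of about 1.02.

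**The case against.** The best defence is that the document already discloses most of this. The sentence after the 19 per group says why six people were excluded and arrives at 32, and the next paragraph itemises them and gives 16 per arm. Nothing says that 38 were randomised, and the 19 can be read as a recruitment target. That stands as far as the counts go. It does not rescue the label: if 19 was a recruitment target, the allowance was for screening failure, and the text gives its purpose as cover for people leaving. Either reading needs a correction.

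Second, the inflation is short by only one person per group, and 19 follows from a common uplift. That also stands, so the inflation is a minor point.

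Third, the harm is hypothetical. The document is retrospective, says the study was completed with 32, and reports no loss after randomisation. That stands too, and it limits the consequence.

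A reader might also infer that the missing reserve would have cut power from 80% to 56–60%. The documents do not support that. The 80% is reproduced by a one-sided test and the 56–60% comes from a two-sided one. About 11 points of that gap (80.0 − 69.3 = 10.7) come from the change of test. Sidedness is a separate gap in the plan, and neither version should be treated as settled.

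**Conclusion.** The point holds as an inconsistency in the stated design. The plan claims 19 per group and a 20% allowance for people leaving. It randomised exactly 16 per group, its own minimum, with a reserve of zero after randomisation. This conclusion depends only on the plan's counts and on the stated order of evaluation and randomisation, not on sidedness. The inflation error is secondary: 19 in place of 20.

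The power figures after a 20% loss (69–72% one-sided, 56–60% two-sided) describe a loss that the text does not report. They assume d = 0.9, equal groups and a t test.

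Two stronger readings are not supported. One is that six people left allocated arms of 19; the flow paragraph shows that they were never allocated. The other is that the analysed sample or the results were damaged; the analysed 32 are the 32 randomised, as far as the text shows. The flow diagram is not available here to confirm this.

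**What to change.** Reword the sample size paragraph to say that 38 people were assessed, 6 were excluded before randomisation (4 ineligible, 2 declined), and 32 (16 per group) were randomised, with no attrition allowance remaining. Remove the statement about 19 in each group, or reword it as a recruitment figure that covered screening exclusions. If the 20% figure is kept, give the inflated size as 16/0.8 = 20 per group and say that it was not reached.

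State whether the test is one-sided or two-sided, and quote power for the 32 randomised on that basis: 80% at d = 0.9 if one-sided; 69% if two-sided, with a detectable d of about 1.02 at 80% power.

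The cost is wording only: no extra patients, no new data and no reanalysis. The stated reserve becomes less favourable, and so does the stated power if the test is two-sided.

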Results: The mean age of the control group was 73.13 ± 3.54 years, and the mean age of the training group was 73.75 ± 5.16 years. In the statistical analysis between groups, the Mini-Mental State Test values were found to be statistically significant in favor of the training group ($p=0.049$). In the intra-group statistical analysis, there was a significant difference in all tests in the training group after the training, while no significant difference was found in the control group.

Conclusions: It was found out that the virtual reality application in individuals with Alzheimer's dementia increased muscle strength and decreased the fall risk. As a result, supporting the physiotherapy and rehabilitation programs with technological developments and virtual reality applications will increase the success of the treatment.

Keywords: Alzheimer's Dementia; Muscle strength; Fall; Virtual reality

Study Procedure and Protocol

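### Does excluding people who missed training or follow-up bias the comparison between the arms?

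*Combined protocol and SAP*

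**What the plan says.** The exclusion sentence in Study Procedure and Protocol mixes baseline conditions with events that happen during the trial. It lists "those who could not be contacted during the follow-up period or who did not participate in the training session" alongside medical history, and closes by saying that "those with a lower or upper extremity amputation at any level were excluded from the study".

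The same section gives the order of events. On the first assessment and enrolment it reads "performed before randomization. 32 individuals suitable for the criteria were included in the study". Sealed-envelope allocation follows, then six weeks of training or no training, then a repeat assessment. For controls, "In the control group, no application was performed during this period, and routine medical treatments were continued", and "the control group was re-evaluated at the end of the 6th week after the first evaluation". They were offered training only once the study was over.

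On numbers, the power calculation gives 16 per group. Three were added to each group for possible leavers, so that "the study was organized with 19 individuals in each group". The text then takes off four people who did not meet the criteria and two who declined, and reports that 32 finished.

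The Statistical Analysis Plan covers software, descriptive summaries, a normality check, the between-group and within-group tests and the 0.05 level. It defines no analysis set and gives no rule for missing week-6 values.

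**The concern.** An eligibility criterion should be decidable before allocation. These two are not, and they differ in reach. Loss of contact can occur in either arm, because both were reassessed at six weeks. Missing the training can occur only in the training arm. Applied literally, the rule would remove the less able or less motivated from one arm and keep their counterparts in the other. That undoes the randomisation, and with no stated analysis set nothing in the plan prevents it.

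The stakes seem higher because the only between-group difference reported as significant, the post-training Mini-Mental State Test, has p=0.049 (Abstract, Results). With a p-value that close to 0.05, one selective removal could decide which side it falls.

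**Working it through.** **Step 1: when each condition can be known, and in whom.**

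| Condition | Known | Can apply to |
|---|---|---|
| Amputation, low cognitive score and similar | at first assessment | anyone screened |
| Not contactable during follow-up | after allocation | both arms |
| Did not take part in training | after allocation | training arm only |

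The structural criticism is therefore correct. The list also mentions cardiac events, cerebrovascular events and infection, which could be read as on-study events, so the count of such conditions is at least two.

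**Step 2: was anyone removed?** All inputs are from Study Procedure and Protocol.

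- Recruitment target: 16 + 3 = 19 per group, and 2 × 19 = 38.
- Not included: 1 (cognitive score below 18) + 3 (hearing or communication problems) + 2 (unwilling to start) = 6.
- Available for randomisation: 38 − 6 = 32.
- Allocated to control: 4 women + 12 men = 16. Allocated to training: 5 women + 11 men = 16. Total 32.
- Reported as finishing: 32.
- Removed after allocation: 32 − 32 = 0.

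The figure of 19 per group does not point to hidden losses. It is the target after the allowance for leavers, and the same six people bring 38 down to 32.

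**Step 3: what the rule does with no removals.** The set with the rule applied and the set of everyone as allocated are the same 32 people. Every test in the Statistical Analysis Plan gives the same result on both. Bias = 0.

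**Step 4: what it could have done.** This is an illustration on assumptions that are not in the documents: no true effect, 16 per arm, the k lowest attenders removed from training, and a correlation ρ between attendance and outcome. The shift in favour of training is ρ times the mean of those who remain (0.1177, 0.2179 and 0.3108 SD for k = 1, 2, 3).

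| k removed | Shift in SD, ρ = 0.3 / 0.5 / 0.7 | Two-sided error |
|---|---|---|
| 0 | 0 / 0 / 0 | 5% |
| 1 | 0.035 / 0.059 / 0.082 | 5.2 / 5.5 / 6.0% |
| 2 | 0.065 / 0.109 / 0.153 | 5.4 / 6.3 / 7.5% |
| 3 | 0.093 / 0.155 / 0.218 | 5.8 / 7.2 / 9.6% |

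Only the first row matches the reported counts. The documents give no attendance data and no attendance threshold, so the other rows cannot be tied to this trial.

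**Step 5: the p=0.049 result.** Assume a two-sided t-test with 16 per arm (df = 30); the plan also allows the Mann-Whitney U test and does not say which was used here. Then t = 2.052 and d = 2.052 × √(2/16) = 0.725. The critical value is t = 2.042, or d = 0.722, a margin of about 0.003 SD. Taking off 0.035 SD gives p of about 0.060. But df = 30 already means that all 16 in each arm were analysed, so nobody was removed and there is no shift to take off. Repeating the sum with 15 against 16 also gives about 0.060, but that contradicts the reported completion count.

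**The case for a change.** The strongest opposing case is that zero removals is partly an inference. The text says how many were allocated and how many finished, but not how many were analysed for each outcome, and it never says that the rule went unused. The wording on 19 per group, followed by the loss of six, can be read as losses after groups had been formed; the two who declined would then be the ones to worry about. The flow diagram, which might settle this, is not visible in the text available here.

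Part of this stands: the number analysed per outcome is not given, and the Statistical Analysis Plan should have named its analysis set. The rest does not. The fuller account places the first assessment before randomisation, describes the two as unwilling to start, and then allocates exactly 16 and 16, itemised by sex. Had two training-arm members been dropped after allocation, 34 people would have been allocated, not 32. A diagram lost in text extraction cannot be counted as missing reporting.

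The p-value argument also proves less than it seems to. A margin of 0.003 SD can be crossed by almost any perturbation, selective or not. That shows that p=0.049 is fragile, which is a separate matter from this rule.

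**Conclusion.** The criterion is misplaced: taking part in training and staying in contact are matters of adherence and follow-up, not eligibility. It has no demonstrated consequence. On the reported counts it removed 0 of 32, the bias is 0, and analysing all participants as allocated would leave every result unchanged. Data collection ended on 30 April 2018 and the statistical analysis is dated 15 May 2018, so there is no future conduct for new wording to protect. Multiple imputation would serve no purpose when no missing week-6 value is reported.

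The conclusion assumes that the stated counts are right and that the 32 who finished are the 32 analysed. A sentence confirming this would be good reporting, but it would alter no estimate or test. If the flow diagram or the data showed fewer analysed than allocated, the concern would become real: the number and reason per arm would need to be disclosed, and all available week-6 data re-analysed by allocated arm. Nothing in the documents points that way.

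### Baseline scores were measured before randomisation, but no balancing is described at allocation and the planned group comparisons do not adjust for them, which loses precision in a trial of 32

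*Combined protocol and SAP*

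**What the plan says.** Study Procedure and Protocol states that the first evaluation was "performed before randomization. 32 individuals suitable for the criteria were included in the study". The method of allocation gets one sentence: "Randomization was performed by the sealed-envelope method". The result was 16 and 16: "4 females and 12 males were determined to be in the control group, while 5 females and 11 males" in the training group. Nothing is said about how the sequence was generated, whether it was blocked or stratified, or who held the envelopes.

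The power analysis in the same section assumes that the effect "will be large ($d = 0.9$), when at least 32 individuals (at least 16 individuals per group) were included in the study". It then allows for dropout: "20% risk rate was determined for the individuals who could leave the study, 3 individuals were added to each group", which makes 19 per group.

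The Statistical Analysis Plan compares the groups by a test of two means, or by Mann-Whitney U where parametric assumptions fail. It names no model with a baseline covariate. Results reports non-significant group differences before training on MMST, right and left knee strength, TFES and TUG. After training, only MMST differs between groups; the Abstract gives p=0.049.

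**The concern.** In a trial of 32 people, a baseline score of the outcome is usually the strongest predictor of the follow-up score. It can be used twice: to balance the groups at allocation, and to remove predictable variation in the analysis. Here the scores were collected before allocation at no extra burden, yet neither use is described.

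Two things are at stake. The first is precision: the unadjusted comparison treats stable differences between residents as noise. The second is how the main finding can be read. The MMST result compares post-training values and lies almost exactly on the significance boundary. Without baseline values by arm, a reader cannot tell how much of the gap was there before training.

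**Working it through.** **Inputs.** From the documents: 16 per group, d = 0.9, 80% power, 0.05 error, MMST p=0.049. Assumed: roughly normal measures; five measures (MMST, right and left knee strength, TFES, TUG); a baseline-to-follow-up correlation r, which the documents do not give.

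**1. The plan's own sample size.** n per group = 2(z_α + z_β)²/d².
- One-sided: 2(1.645 + 0.842)²/0.81 = 15.3, so 16. This reproduces the stated figure (t-test power 80.0%).
- Two-sided: 2(1.960 + 0.842)²/0.81 = 19.4, so 20 (21 with the t-test). Power at 16 per group is 69.3%.

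The plan does not state sidedness. That is a separate matter, but about 70% is the starting point for an unadjusted two-sided test.

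**2. Chance imbalance at baseline.** Under unrestricted 16:16 allocation, the difference in means, in SD units, has standard error √(2/16) = 0.354.

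| Gap exceeds | Chance, one measure |
|---|---|
| 0.25 SD | 48% |
| 0.5 SD | 15.7% |
| 0.75 SD | 3.4% |

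The chance that at least one of five measures differs by more than 0.5 SD is 1 − (1 − 0.157)⁵ = 57.5% if they are independent, and about 48% if they correlate at 0.5 (simulation).

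**3. What stratification buys.** In simulation, a median split on MMST cuts the chance of an MMST gap above 0.5 SD from 15.7% to about 2%. It does little for the other measures: the any-of-five figure falls only from 48-58% to 38-51%.

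**4. What adjustment buys.** Adjusting for baseline multiplies the standard error by √(1 − r²). Two-sided power at d = 0.9:
- r = 0.5: SE = 0.354 × 0.866 = 0.306; 0.9/0.306 = 2.94; power about 80%.
- r = 0.7: SE = 0.354 × 0.714 = 0.252; 0.9/0.252 = 3.56; power about 93%.

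By simulation, stratified allocation with only the two-level stratum in the model gives 76-85%. Stratifying and then ignoring the stratum adds little and makes the test conservative.

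**5. How close the MMST result is.** If a t-test was used, p=0.049 on 30 degrees of freedom means t = 2.052, and 2.052 × 0.354 = 0.725 SD. The threshold is 2.042 × 0.354 = 0.722 SD, so the result clears it by 0.003 SD. A 0.5 SD baseline gap carries r × 0.5 into the follow-up values: 0.25 SD at r = 0.5 and 0.35 SD at r = 0.7, or 34% to 48% of 0.725.

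**6. What the baseline tests show.** With 16 per arm, any gap below about 0.72 SD gives p>0.05. Non-significance therefore does not rule out a gap of 0.5 SD.

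**The case against.** The strongest reply is that chance imbalance is not bias. Under random allocation the unadjusted t-test already allows for it; in simulation at r = 0.7 its false-positive rate stays near 5%. The reported baseline comparisons are all non-significant, and no imbalance has been shown. This stands: the point concerns precision and fragility, and a reader who infers that the MMST result is biased goes beyond the documents.

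It can also be said that absence of stratification is inferred from silence. That stands too. The sex split of 4 and 5 women fits either kind of allocation, and the CONSORT diagram is not in the text available. What can be said is that no balancing is described. The missing baseline covariate does not depend on this, since the Statistical Analysis Plan names its between-group tests.

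A reader might further infer a fixed set of 16 + 16 envelopes whose last allocations could be guessed. The documents do not support this. The power analysis says "it was calculated that at least 16 individuals could be included in each group", but the study was then organised for 19 per group, and equal final counts do not establish a fixed set. Nothing says that envelopes were opened one by one or who held them. If all 32 were assessed and included first, guessing could not change who entered. Even granting a fixed set opened in sequence, the best guesser expects 19.1 correct of 32 against 16 by chance.

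Finally, the data were collected and analysed in 2018, so allocation cannot be changed. That is true of allocation but not of the analysis.

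**Conclusion.** The concern holds as a loss of precision at a modest cost to remedy. As described, the plan uses the pre-randomisation scores in neither allocation nor between-group comparison. The chance of a baseline gap above 0.5 SD is about 16% per measure, if allocation was an unrestricted 16:16 draw. Adjustment would raise two-sided power at d = 0.9 from about 70% to 80-93%, if r lies between 0.5 and 0.7. Because eligibility confined MMST to 18-24, its correlation could be lower and the gain smaller: at r = 0.3, SE = 0.354 × 0.954 = 0.337 and power is about 73%.

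The p=0.049 for MMST should be read as fragile. Adjustment could move it either way, and the documents do not show which. The 0.725 SD figure assumes a t-test; the text does not say whether that or Mann-Whitney was used.

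**What to change.** **For the completed trial.** Analyse MMST, right and left knee strength, TUG and TFES each with an ANCOVA of the six-week value on group and that outcome's own baseline value. Report the adjusted difference with its 95% confidence interval, labelled as post hoc because the unadjusted results are known. Report baseline MMST, knee strength, TUG and TFES by arm with the size of each difference rather than a p-value alone. The cost is a reanalysis of data already held.

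**For any repeat.** Suggested wording: *After first evaluations are complete, the coded list of eligible participants is allocated in one step from a computer-generated 1:1 list, stratified by baseline MMST (at or below / above the median). Each outcome is compared between groups by ANCOVA including its own baseline value.* Baseline must stay in the model: stratification alone adds little power, and stratifying on MMST leaves the other measures largely unbalanced. No extra participants or visits are needed. The small downside is that, with recruitment in batches, each batch must finish its first evaluation before allocation.
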